10.9. Sensitivity Analyses

A quantitative bias analysis will be used to assess the sensitivity of the estimates to violations of the assumption of no unmeasured confounding. To conduct this analysis, it will be assumed that the hazard ratio is a reasonable approximation of the odds ratio, and then previously published formulas for the relation of unadjusted or partially adjusted to adjusted odds ratios will be used to estimate the effect, given inputs for the strength of the confounder treatment and confounder outcome relationships (Lash 2021). The analysis will be conducted across a range of values for the input parameters to assess how much the effect changes given different confounder relationships. Specifically, given the (adjusted for known confounders) odds ratio for the association between the unmeasured confounder and the outcome (OR_{DZ}) and the prevalence of the confounder among the OCA-treated (P_{Z1}) and non-OCA-treated (P_{Z0}) (each assumed

homogeneous across levels of known confounders), the relationship between the partially adjusted and fully adjusted odds ratios is $\frac{OR_{partial}}{OR_{full}} = \frac{OR_{DZ}P_{Z_1} + 1 - P_{Z_1}}{OR_{DZ}P_{Z_0} + 1 - P_{Z_0}}.$

10.10. Assessment of Claims-based PBC Definition

The Komodo Health data are claims-based. Per AASLD guidelines, PBC diagnosis is based on the presence of ≥ 2 of 3 diagnostic factors:

- History of elevated ALP levels for at least 6 months
- Positive AMA titer
- Liver biopsy finding consistent with PBC

AMA is normally assessed once to diagnose PBC, and the test may have occurred years prior to entry into the Komodo Health claims database. Indeed, a preliminary analysis shows that $\sim 10\%$ of patients with a PBC diagnostic code have an AMA test result in the database. As AMA cannot be used in the definition of PBC, a claims-based analysis will be used to identify PBC patients in claims data requiring 2 outpatient claims or 1 inpatient claim based upon the work of Meyers (Meyers 2010).

Using Canadian ambulatory care and inpatient records, Meyers found that a 2-outpatient claim algorithm had 89% positive predictive value (PPV) when compared to AMA-verified definite, probable, or suspected PBC. A single inpatient claim had 81% PPV, with limited incremental benefit of 2 claims (86% PPV).

In these studies, in addition to the claims criteria, evidence of UDCA use is required, which the Sponsor believes will further improve the PPV of the claims-based algorithm. To validate this approach, the Sponsor will conduct sensitivity and specificity analyses using AMA as the gold standard of PBC diagnosis within the Komodo Health database. The subpopulation of patients with AMA test results (positive vs negative) will be compared to those with a positive and negative diagnosis by the claims + UDCA definition. The sensitivity of the non–AMA-based definition will be defined as the proportion of patients classified as having PBC with the gold standard definition who are also classified as having PBC with the non–AMA-based definition. The negative predictive value of the non–AMA-based definition will be defined as the proportion of patients not classified as having PBC with the non–AMA-based definition who are also not classified as having PBC with the gold standard definition. The specificity and PPV will be assumed to be equal to 1, as the non–AMA-based definition will capture a subset of those individuals classified as having PBC by the gold standard definition.

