The only approved drug therapy for PBC has been the bile acid ursodeoxycholic acid (UDCA), a physiological constituent of human bile (Lindor 2009). While UDCA therapy had a marked effect on the treatment of PBC, up to 40% of patients showed a suboptimal response or no response to UDCA (Corpechot 2008, Kumagi 2010). Such patients were at significantly increased risk of a poor clinical outcome due to PBC disease progression. Obeticholic acid (OCA) is a farnesoid X receptor (FXR) agonist and a modified bile acid that is derived from the primary bile acid chenodeoxycholic acid (CDCA), the natural human FXR ligand. OCA (Ocaliva[®]) has received marketing authorization in the US, the European Union (EU), and several other countries for the treatment of PBC in combination with UDCA in adults with an inadequate response to UDCA or as monotherapy in adults unable to tolerate UDCA. In the US, Ocaliva is contraindicated in patients with decompensated cirrhosis (eg, Child-Pugh Class B or C), a prior decompensation event, complete biliary obstruction, or compensated cirrhosis with evidence of portal hypertension. Approval in the US and the EU was based on a surrogate endpoint (reduction in ALP), and as part of regulatory commitments in these regions, the following postmarketing studies were initiated: Study 747-302, a Phase 3b/4 study designed to prospectively obtain evidence to confirm clinical benefit in PBC subjects, and Study 747-401, a Phase 4 study designed to evaluate the pharmacokinetics (PK) and safety of OCA in PBC subjects with hepatic impairment. Both 747-302 and 747-401 terminated early, due to the challenges of recruitment and long-term retention of patients with a rare disease subsequent to Ocaliva regulatory approval. Changes to endpoints and statistical analysis plans to accommodate low recruitment, low events rates, and early termination may necessitate the need for clinical trial data to be supplemented with real-world evidence, with the goal of providing regulators with a more complete evidence package characterizing the efficacy and safety of OCA in patients with PBC.

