7.2. Inclusion Criteria

A patient who meets **all** of the following criteria for a given index date is eligible for inclusion:

- Definite or probable PBC diagnosis
 - Global PBC Registry (consistent with American Association for the Study of Liver Diseases [AASLD] and the European Association for the Study of the Liver [EASL] practice guidelines; Lindor 2009, EASL 2009): presence of ≥2 of the following 3 diagnostic factors:
 - History of elevated ALP levels for at least 6 months
 - Positive antimitochondrial antibody (AMA) titer
 - Liver biopsy finding consistent with PBC
 - Komodo Health claims data: one of the following (Meyers 2010):
 - ≥1 inpatient claim with a PBC admission diagnosis at any position (ie, primary, secondary diagnosis, etc.)
 - ≥ 2 outpatient claims with a PBC diagnosis on separate days
- Inadequate response or intolerance to UDCA (see definitions in Section 7.1)
- Age ≥ 18 years at the index date
- Continuous enrollment and evaluable data for at least 12 months before the index date (inclusive)

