In the event this produces 2 patients with one token (called a "collision") or one patient with 2 tokens, Datavant will then match on social security number and/or address (when available in the dataset). In the overall Komodo Health claims database, in the match with the NDI, and in the match with Quest Diagnostics data, this has produced 99% exact match. In the subset of

PBC patients, only 873 of 164,942 patients are flagged as a collision and have been removed from analysis. The same process will be used with the OPTN transplant data.

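### Komodo study (747-405): PBC is identified by claims codes with cited PPVs of 81% to 89%, but the only planned check assumes a PPV of 1 and nothing carries a possible between-group difference in false positives into the hazard ratio

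*Combined protocol and SAP*

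**What the plan says.** Section 7.2 admits a Komodo patient on "≥1 inpatient claim with a PBC admission diagnosis at any position", or on two outpatient claims on separate days. The rule is the same for both groups. The registry study (747-404) instead requires two of three clinical diagnostic factors.

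Section 10.10 takes its accuracy figures from an outside Canadian validation study: "a 2-outpatient claim algorithm had 89% positive predictive value (PPV"), and "A single inpatient claim had 81% PPV, with limited incremental benefit of 2 claims (86% PPV"). It adds that "evidence of UDCA use is required, which the Sponsor believes will further improve the PPV of the claims-based algorithm", without giving a figure. Section 7.1.1 also requires ALP and/or bilirubin above the ULN, and Section 7.3 excludes several other liver diseases.

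The planned validation compares the claims + UDCA definition with AMA results, which about 10% of PBC-coded patients have. It reports sensitivity and negative predictive value. Specificity and PPV are set to 1, on the ground that the claims-defined patients form a subset of those the gold standard calls PBC. The synopsis lists this check among the sensitivity analyses, but it produces no hazard ratio.

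Section 10.9 states its purpose as follows: "A quantitative bias analysis will be used to assess the sensitivity of the estimates to violations of the assumption of no unmeasured confounding". No subgroup in Section 10.8 and no weighting covariate in Section 10.1.1 concerns AMA status or diagnostic certainty. Section 4.1 describes OCA as authorised "for the treatment of PBC in combination with UDCA in adults with an inadequate response to UDCA" or, for patients who cannot tolerate UDCA, as monotherapy.

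**The concern.** A control enters on codes, some UDCA exposure and one raised ALP or bilirubin. An OCA patient meets the same rule and has also been prescribed a drug authorised for PBC. It is reasonable to suspect that the share of patients without PBC is larger among controls. Such patients may have a different risk of death or hepatic admission, and the control hazard would then not be that of comparable PBC patients.

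The plan cannot show whether this happens. The one check of the definition fixes at 1 the quantity in question, in the section that cites 81% to 89% for the underlying codes. Even a correct PPV would feed no hazard ratio. What is at stake is how the primary Komodo HR is read, and whether its agreement or disagreement with the registry study, which uses a clinical definition, reflects OCA or diagnostic coding.

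**Working it through.** **Inputs from the documents.** PPV 89%, 86% and 81% (10.10); 395 OCA and 5916 control patients, alpha 0.05, event rates 5% to 15%, VIF 1.05 to 2.0 (10.4); two-sided test (10.3.1); AMA result in about 10% (10.10). The PPVs are cited without cell counts, so they cannot be rebuilt.

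**Assumed, not in the documents.** The false-positive shares P_Z1 (OCA) and P_Z0 (control), and RR, the hazard of false positives relative to true-PBC controls.

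**Step 1: bias factor.** With no true effect,

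observed HR = [(1 − P_Z1) + P_Z1 × RR] / [(1 − P_Z0) + P_Z0 × RR].

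This is the 10.9 formula with Z = not PBC and RR in place of OR_DZ. With P_Z1 = 0:

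| P_Z0 | RR 1/3 | RR 0.5 | RR 1 | RR 2 | RR 3 |
|---|---|---|---|---|---|
| 5% | 1.03 | 1.03 | 1.00 | 0.95 | 0.91 |
| 11% (PPV 89%) | 1.08 | 1.06 | 1.00 | 0.90 | 0.82 |
| 19% (PPV 81%) | 1.15 | 1.10 | 1.00 | 0.84 | 0.72 |

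Example: P_Z0 = 11%, RR 3 gives 1 / (0.89 + 0.33) = 1/1.22 = 0.82.

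**Step 2: only the between-group difference matters.** If P_Z1 = P_Z0, numerator and denominator are equal and the factor is 1 for every RR. With P_Z1 = 5% and P_Z0 = 11%, the factor is 1.10/1.22 = 0.90 at RR 3 and 0.975/0.945 = 1.03 at RR 0.5. Counts alone show nothing. At a PPV of 89% in both groups there would be 0.11 × 5916 = 651 false-positive controls and 0.11 × 395 = 43 in the OCA group, with no bias of this kind.

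**Step 3: effect on the test.** The set-up was first checked against the power statement in 10.4. For HR 0.5 at VIF 2.0 and a 9% event rate, effective events are 0.09 × 6311 / 2.0 = 284. The allocation term is (395/6311) × (5916/6311) = 0.0587, and z = 0.693 × √(284 × 0.0587) − 1.96 = 0.87. Power is 80.8%, against a stated adequacy above 9%. At VIF 1.5 the 80% threshold is 6.7%, against a stated 6%. The set-up is close enough for illustration.

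Now take true HR = 1, a 10% event rate and VIF 1.5. Effective events are 631/1.5 = 421, and √(421 × 0.0587) = 4.97. The chance of a significant result favouring OCA is P(Z > 1.96 − 4.97 × |ln factor|), against a nominal 2.5%:

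- P_Z0 = 5%, RR 3: P(Z > 1.49) = about 7%
- P_Z0 = 11%, RR 2: 7.5%; RR 3: 17%
- P_Z0 = 19%, RR 3: 36%
- P_Z0 = 11%, RR 0.5: about 1%, because the bias then runs against OCA

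**Step 4: what AMA data can supply.** If the 10% holds in both groups, about 40 OCA and 592 control patients have a result. At a PPV of 89% the control estimate has a 95% half-width of 1.96 × √(0.89 × 0.11 / 592) = 2.5 points. In the OCA group, even 40 positive out of 40 leaves an exact 95% lower limit of 0.025^(1/40) = 91%. An HR re-estimated in these patients alone would have about 19% power for HR 0.5 at a 10% event rate and VIF 1.5. It could only be descriptive.

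**The case against.** Much of the opposing case stands.

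- The cited PPVs are not those of the analysed cohort. UDCA use, a raised ALP or bilirubin and the exclusions all come on top. A share of 19% would also need every control to enter through a single inpatient claim and the later filters to remove nobody without PBC. The filters are not complete (Appendix A marks the ICD-10 code for primary sclerosing cholangitis as 2019-2021 only, and lists no ICD-9 code under that name), but they probably raise the PPV.
- The factors above are crude. SMR weighting and Cox adjustment cover age, sex, liver biochemistry, platelets, time since UDCA failure, portal hypertension, cirrhosis, Charlson score and insurance type. The relevant share and RR are those left after weighting and adjustment, and may be smaller.
- The 10.9 formula can already carry this problem. That makes the remedy cheap, but the plan names no such use.
- The registry study is a comparison free of claims coding. It is analysed separately, however, and does not correct the Komodo HR. The Clean Room Committee may change definitions before unblinding, but a power to change them is not a pre-specified analysis.

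Three stronger readings are tempting and unsupported. A reader might infer that false positives lie almost only among controls. Both groups face one rule and no PPV by group is given, so this remains an inference from the OCA indication. A reader might infer that the bias favours OCA; that holds only if the residual RR exceeds 1. And a reader might take over-coding from Section 12.3, where "only 873 of 164,942 patients are flagged as a collision", set against 325 million Komodo patients (12.1.1) and the cited prevalence of 40 per 100,000 (4.1). That count accumulates over several years, and its patients are not shown to have met the study's criteria. It says nothing about the false-positive share among eligible controls.

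**Conclusion.** The point holds in limited form. The plan sets PPV to 1 while citing 81% to 89% for the underlying codes, and no planned analysis shows what diagnostic error would do to the Komodo HR. Whether the HR is biased is unknown. Bias of this kind needs a between-group difference in false-positive share and a residual RR other than 1. At a control share of 5% the shift is modest (0.91 to 1.03 for RR 3 to 0.5). At 11% it matters (0.82 to 1.06). The 19% figures mark an outer limit and are not an expectation. All rest on an OCA-group PPV of 1, no true effect, and assumed values of share and RR. This is a gap in planned sensitivity analysis that should be closed; it does not show that the primary result would be wrong. It concerns Komodo only.

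**What to change.** Before outcomes are released under Section 10.1.2, for Komodo only:

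1. **Section 10.10.** Replace the assumed PPV of 1 with the PPV estimated among AMA-tested patients who meet the claims + UDCA definition, with a confidence interval, by treatment group where numbers allow. The planned cross-tabulation already holds the cells. State that 1 − PPV against AMA tends to overstate the false-positive share, because the two-of-three rule permits AMA-negative PBC, and that the roughly 10% with a result may not be representative.
2. **Section 10.9.** Add a diagnosis-misclassification table using the existing formula with Z = not PBC. Vary P_Z0 from 0 to the estimated 1 − PPV, with 19% as an extreme; vary P_Z1 from 0 up to P_Z0; and take RR over a range symmetric on the ratio scale, such as 1/3 to 3. Divide the observed HR by the factor, and state that shares and RR refer to the weighted, adjusted comparison.
3. **Optional, supportive only.** Rerun the weighted primary analysis requiring at least two PBC claims on separate days by the index date in both groups. It may barely change the cohort and cannot isolate a between-group difference in error.

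Items 1 and 2 cost one cross-tabulation and a small table. Item 3 costs one rerun of existing code and the loss of some controls and possibly some OCA patients.

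### Section 10.10 sets the specificity and PPV of the claims + UDCA definition to 1 by assumption, so no defined measure can detect false-positive classification against AMA

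*Combined protocol and SAP*

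**What the plan says.** Section 10.10 of the combined protocol and SAP explains that AMA is usually tested once, often before a patient enters the claims database, and that only about 10% "of patients with a PBC diagnostic code have an AMA test result in the database". It continues: "As AMA cannot be used in the definition of PBC", a claims-based rule is used instead (two outpatient claims or one inpatient claim). In addition, "evidence of UDCA use is required, which the Sponsor believes will further improve the PPV of the claims-based algorithm".

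To validate this, "the Sponsor will conduct sensitivity and specificity analyses using AMA as the gold standard of PBC diagnosis within the Komodo Health database". The layout is given: "The subpopulation of patients with AMA test results (positive vs negative) will be compared to those with a positive and negative diagnosis" under the claims + UDCA definition. Sensitivity and NPV are then defined in words. The other two measures are not estimated: "The specificity and PPV will be assumed to be equal to 1", on the ground that the definition "will capture a subset of those individuals classified as having PBC by the gold standard definition".

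The Synopsis (Sensitivity Analyses) lists this comparison as the assessment of how the claims-based definition performs, with AMA as gold standard.

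**The concern.** The section promises a specificity analysis and sets up a table in which specificity and PPV can be observed. It then replaces both with their best possible value.

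PPV is also the measure on which the section's own argument turns: the UDCA requirement is defended by the expectation that it raises PPV. If PPV is fixed at 1, that expectation cannot be checked, and a reader of the report could take an assumption for a validation result. The definition in question selects the whole Komodo cohort (Study 747-405).

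**Working it through.** **Step 1. Does the subset relation follow from anything in the documents?** PPV = 1 and specificity = 1 against AMA require that no tested, definition-positive patient is AMA-negative. The relevant statements are:

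- Section 7.2 (Komodo): at least one inpatient PBC claim or at least two outpatient PBC claims on separate days. No AMA result is needed. Section 10.10 adds evidence of UDCA use. Neither condition forces a positive AMA.
- Section 10.10, diagnostic rule: two of three factors (sustained ALP elevation, positive AMA, compatible biopsy). ALP plus biopsy is enough, so PBC without positive AMA is allowed.
- Section 10.10, UDCA: the sponsor believes it will improve PPV further. A quantity that is expected to improve is not already known to be 1.
- Section 10.10, cited Canadian validation study: the two-outpatient-claim algorithm "had 89% positive predictive value (PPV) when compared to AMA-verified definite, probable, or suspected PBC"; the inpatient figures are 81% for one claim and 86% for two. These are claims-only values against a different reference standard, so they do not predict PPV here. They also give no support for the value 1.

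Reading the gold standard as the full two-of-three rule does not rescue the relation. Inclusion rests on claims and UDCA use, not on two documented diagnostic factors.

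**Step 2. Which cells do the defined measures use?** Among AMA-tested patients, let a = AMA+/definition+, b = AMA−/definition+, c = AMA+/definition−, d = AMA−/definition−.

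- Sensitivity = a/(a+c): defined in the plan, no b.
- NPV = d/(c+d): defined in the plan, no b.
- PPV = a/(a+b): assumed 1, which is the same as b = 0.
- Specificity = d/(b+d): assumed 1, which is the same as b = 0.

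**Step 3. Numerical check.** The cell counts are hypothetical: a = 800, c = 200, d = 300.

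| b | Sensitivity | NPV | PPV | Specificity |
|---|---|---|---|---|
| 0 | 800/1000 = 0.80 | 300/500 = 0.60 | 800/800 = 1 | 300/300 = 1 |
| 100 | 800/1000 = 0.80 | 300/500 = 0.60 | 800/900 = 0.89 | 300/400 = 0.75 |

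The two planned measures are identical in both rows.

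**Step 4. Does the sampling frame matter?** The section restricts the analysis to patients with AMA results but does not say whether tested patients without a PBC code are included. Such patients cannot meet the definition. Including them adds, say, e to c and f to d and leaves a and b alone:

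- PPV = a/(a+b): unchanged.
- Sensitivity = a/(a+c+e), specificity = (d+f)/(b+d+f), NPV = (d+f)/(c+e+d+f): all change.

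So the frame affects three of the four measures, including both that the plan does estimate.

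**Step 5. Could the data test the assumption?** The number of AMA-tested patients who meet the definition is not given, so precision cannot be stated. The number n needed for a 95% chance of seeing at least one AMA-negative patient, if the true fraction is q, is ln(0.05)/ln(1−q), rounded up. For assumed q = 5% this is 59; for q = 1% it is 299. For scale, about 10% of the more than 100,000 PBC-coded patients (Section 6.2) is roughly 10,000 AMA results before the claims and UDCA filters. About 3% of those (299/10,000) would have to meet the definition to reach 299. This speaks only to feasibility, not to the size of the problem.

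**The case against.** The strongest reply is that AMA alone is not a true gold standard. Under the two-of-three rule an AMA-negative, definition-positive patient may well have PBC, so an estimated PPV below 1 would partly measure AMA negativity rather than misdiagnosis. That is correct. It is a reason to label the estimate carefully, not to set the cell to zero. The section itself names AMA as the standard, and a comparison against it should report what it shows.

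Several stronger readings are tempting but not supported:

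- *That AMA-negative, definition-positive patients would be hidden altogether.* The planned comparison of positives and negatives could well be shown as a cross-tabulation, which would display them. The text supports only that no defined measure uses them.
- *That the true PPV is 81% to 89%.* Those figures come from claims without UDCA, Canadian records and another reference standard.
- *That the validation target is contradictory.* Sections 12.1.4 and 12.1.5 say that AMA data validate the ICD-10 claims criteria, while Section 10.10 tests claims + UDCA. The former reads naturally as shorthand for the latter.
- *That the lack of an AMA shell in Appendix B shows an omission.* The shells are not exhaustive; the component analyses, subgroups and bias analysis have none either.
- *That the hazard ratio is biased.* Nothing here shows that. The analysis is supportive and leaves the primary estimator untouched.

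**Conclusion.** The point stands as a fault in a supporting analysis and should be corrected. Section 10.10 announces specificity analyses and then fixes specificity and PPV at 1 on a subset rationale for which the documents offer no basis. Two of the four accuracy measures become assumptions, and the two that remain cannot respond to false-positive classification against AMA.

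The algebra is exact and needs no assumption. The shift from 1 to 0.89 (PPV) and 0.75 (specificity) belongs to a hypothetical table. The actual size is unknown because the documents do not give the cell counts. The consequence is confined to what can be claimed about the Komodo PBC definition.

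**What to change.** In Section 10.10:

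1. Delete the assumption that specificity and PPV equal 1, together with the subset rationale.
2. Report the observed 2x2 table of the claims + UDCA definition by AMA result among AMA-tested Komodo patients, with estimated sensitivity, specificity, PPV and NPV and their 95% CIs.
3. State whether AMA-tested patients without a PBC code are included.
4. Describe 1 − PPV as the AMA-negative fraction among tested, definition-positive patients, not as the proportion without PBC. Add that AMA alone is an imperfect standard and that the roughly 10% with a result may not represent the rest.

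Optionally, give the same table for the claims-only definition in the same patients, so that the belief about UDCA can be checked. This is an extra analysis and is not needed to remove the contradiction.

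The cost is one revised paragraph and one table (two with the option), using AMA data already planned for this purpose. The downside for the sponsor is that reported specificity and PPV may fall below 1.
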